8.3.7. Information on COVID-19

The investigator will confirm the presence or absence of the onset of COVID-19 during the observation period and enter the information.

- Presence or absence of COVID-19 onset (“present” should be selected if there are symptoms, and “absent” if there are no symptoms)

If the onset of COVID-19 is “present,” the following information should also be entered.

- Date of diagnosis of COVID-19
- Presence or absence of actions/procedures taken (administration of COVID-19 treatment drugs*, hospitalization, oxygen administration, ICU admission, use of mechanical ventilation, use of ECMO)

*: Treatment drugs with an indication for use in SARS-CoV-2 infection

- Outcome (resolved/recovered, resolved with sequelae, death, not resolved, and unknown) and date of outcome

The outcome should be followed up as much as possible even after the end of the observation period.

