8.7.4. Analysis of Information on COVID-19

By using the information on COVID-19 entered in the CRF submitted by the investigator, participants who are considered to be in a severe condition will be identified, and the number and proportion of the participants will be tabulated with reference to the severity classification in the "Guidance for Treatment of Novel Coronavirus Infection (COVID-19)." Exploratory analyses will be performed as needed.

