8.2.3.4. Information about COVID-19

Using the safety analysis set, participants underwent or not underwent any COVID-19 pathogen test (nucleic acid detection test [PCR/LAMP], antigen test) will be summarized. Among participants underwent nucleic acid detection test or antigen test, those with each result (positive or negative) will be summarized in terms of n and proportion. Furthermore, positive participants will be summarized by kind of test in terms of n and proportion, and positive participants developing COVID-19 will be summarized by n and proportion. In addition, participants with severe COVID-19 will be summarized in terms of n and proportion (denominator = the number of participants with COVID-19) with severe cases being defined as any of the following actions taken during the period from disease onset to the outcome date:

- Admission to the ICU
- Use of mechanical ventilation
- Use of ECMO

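### SAP 8.2.3.4 counts severe COVID-19 by three procedures only, so a COVID-19 death without any of them is missed by the severe count, and COVID-19 outcome is tabulated nowhere

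*SAP*

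**What the plan says.** Protocol 8.3.7 has the investigator record, for each child with onset of COVID-19, the date of diagnosis and whether any of six actions was taken: COVID-19 treatment drugs, then "hospitalization, oxygen administration, ICU admission, use of mechanical ventilation, use of ECMO". As a separate item it records "Outcome (resolved/recovered, resolved with sequelae, death, not resolved, and unknown) and date of outcome", to be followed as far as possible beyond the observation period.

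Protocol 8.7.4 says that, from the COVID-19 information in the CRF, "participants who are considered to be in a severe condition will be identified" and counted "with reference to the severity classification in the" Japanese treatment guidance cited there. The documents do not reproduce that classification.

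SAP 8.2.3.4 turns this into a rule, "with severe cases being defined as any of the following actions taken during the period from disease onset to the outcome date". Three actions follow: first "Admission to the ICU", then "Use of mechanical ventilation", then ECMO. The severe cases are reported as a count and as a share of the COVID-19 cases ("denominator = the number of participants with COVID-19"). The outcome date closes the time window, but the outcome itself is not used.

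**The concern.** The list is closed, and death is not on it. If a child with COVID-19 died without ICU admission, ventilation or ECMO, the only planned summary of COVID-19 severity would count that child among the cases but not among the severe ones. The error can run in one direction only: the rule can understate the severe proportion through this gap but cannot overstate it. COVID-19 is one of the three kinds of information named in the study objective (Protocol 7, SAP 2.1), and the item needed to close the gap is already on the CRF.

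**Working it through.** The plan gives no figure for this point: neither an expected number of COVID-19 cases nor an expected severe proportion. Its one calculation, the 83% chance of seeing an event of 3% incidence among 60 children, comes out at 1 − 0.97^60 = 0.839 and has no bearing here. The check is to apply the rule to a case and then look for the death in the other planned outputs.

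**Step 1: apply SAP 8.2.3.4.** Take a child with COVID-19 whose recorded outcome is death and who had no ICU admission, ventilation or ECMO.
- Denominator (participants with COVID-19): the child counts as 1.
- Severe numerator (any of the three actions): the child counts as 0.

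Only deaths with none of the three actions are affected. Ventilation is not tied to a place of care, so a death in an emergency room or on a ward after ventilation already counts as severe.

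**Step 2: look for the death elsewhere in the SAP.**
- SAP 8.2.3.2.1 tabulates serious adverse events by SOC and PT, without outcome.
- SAP 8.2.3.1.3 breaks events down by outcome, including death, but only for adverse reactions. A COVID-19 death judged unrelated to the vaccine would not enter.
- SAP 8.2.1.2 tabulates reasons for discontinuation at the end of the observation period. Death is one of the reasons (Protocol 8.3.4), but it is not linked to COVID-19, and a death after that period could be absent.
- SAP 9 lists participants with serious adverse events. It names no separate listing of COVID-19 cases.
- SAP 8.2.3.4 summarises tests, positives, onset of COVID-19 and severe cases. It has no row for COVID-19 outcome, and no other section has one.

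The death would be visible, but no summary would join it to COVID-19.

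**Step 3: size, as an illustration only.** Assume k COVID-19 cases, exactly one of them such a death, and no other severe case. The rule as written gives 0/k; counting death gives 1/k. The exact 95% limits use the method in SAP 8.1.3. For 0/k the upper limit is 1 − 0.025^(1/k). For 1/k the lower limit is 1 − 0.975^(1/k), and the upper limit is the 97.5% quantile of a beta(2, k − 1) distribution.

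| Assumed k | Rule as written | Death counted |
|---|---|---|
| 3 | 0/3 = 0% (0 to 70.8%) | 1/3 = 33.3% (0.8 to 90.6%) |
| 6 | 0/6 = 0% (0 to 45.9%) | 1/6 = 16.7% (0.4 to 64.1%) |
| 10 | 0/10 = 0% (0 to 30.8%) | 1/10 = 10% (0.3 to 44.5%) |

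The point estimate moves visibly because the denominator is COVID-19 cases, not all 60 children. The intervals overlap heavily in every row.

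**The case against.** The case for leaving the rule alone has real weight.

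- **The guidance may grade by care given.** Protocol 8.7.4 ties severity to an external classification, and the CRF keeps actions and outcome as separate items. A severity measure built on actions, with death held as an outcome, is a possible design. This stands. A reader might infer that the SAP contradicts Protocol 8.7.4 whatever the guidance says, but the documents do not support that, because the classification cannot be read from them.
- **No one is labelled non-severe.** SAP 8.2.3.4 prints only the severe n and proportion. This stands: the case would be absent from a numerator, not placed in a favourable category.
- **The death would be reported anyway.** Death makes an event serious (Protocol 8.3.8.2 and 10.4.2), a fatal event must be notified to the sponsor immediately (Protocol 10.1), and serious events are tabulated and listed. A reader might infer that a death could be hidden, and it could not. What remains is that none of these outputs corrects the severe proportion or counts COVID-19 deaths.
- **VAED/VAERD is unaffected.** It is a listed potential risk, so a reader might infer that this gap weakens its detection. SAP 8.2.3.1.4 gives it a separate definition by coded terms, to which the severe COVID-19 rule does not contribute.
- **Nothing is decided on this proportion.** There are no hypothesis tests or decision rules (SAP 4), and severe COVID-19 is not among the safety endpoints in SAP 6.1. This stands, and it sets the priority.

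**Conclusion.** The point holds as a gap in a stated counting rule. A COVID-19 death without ICU admission, ventilation or ECMO enters the denominator and not the severe count, and the collected COVID-19 outcome is summarised nowhere in the SAP.

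The expected effect is near zero, since it takes a COVID-19 death with none of the three actions among about 60 children observed for 28 days. No result is shown to be wrong. If one such death occurred, the severe proportion would read 0/k instead of 1/k. The values of k used above are assumptions, because the documents give no number of cases. Whether the cited guidance counts death as severe is unknown from the documents, and the conclusion does not say that it does. Low priority.

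**What to change.** In SAP 8.2.3.4:
1. Keep the three-action count as its own row, and state how it maps to the classification named in Protocol 8.7.4.
2. Add a row labelled *severe or fatal COVID-19*: any of the three actions, or COVID-19 outcome recorded as death, over the same denominator.
3. Tabulate COVID-19 outcome beside these rows, using the five categories in Protocol 8.3.7.

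The cost is one extra row, one small table and a sentence of definition. No new data and no change to the CRF or sample size are needed, and no error rate is affected. If the guidance classification does not count death, the new row goes slightly beyond it. The label makes that plain, and the retained three-action row preserves the link. SAP version 2.0 is dated 14 June 2024 and database release was planned for 24 September 2024 (Protocol 5). If the tables have already been produced, the outcome table can be added and marked as a later addition.

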8.2.3.5. Subgroup analyses

Participants with at least one adverse reaction will be summarized in terms of n and proportion by each factor defined in Section 5.4.

For subgroup analyses regarding hepatic impairment and renal impairment, if judged to be necessary (Section 5.4), adverse reactions will be summarized by SOC and PT in terms of n and proportion. For reactogenicity events, local reactions of maximum severity (by local reaction, any local reaction) will be

summarized in terms of n and proportion (by severity, any severity). Systemic reactions will be summarized in the same manner.

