8. RESEARCH METHODS

8.1. Study Design

This is a multicenter cohort study. The investigator will record information required by this study in case report forms (CRFs) based on information obtained from the preliminary examination sheet or medical interviews, etc., and records such as medical records. A health observation diary will be distributed to vaccinated individuals participating in this study, and they will be requested to record information on reactogenicity events (local reactions and systemic reactions, including pyrexia) after vaccination with this product.

The investigator will collect the health observation diary after the end of the observation period of each CRF, and check the details of records other than symptoms at the vaccination site and general symptoms specified in the diary (including the information on COVID-19) as needed and record them as adverse events. The investigator should record the symptoms at the vaccination site (local reactions) and general symptoms including pyrexia (systemic reactions) specified in the health observation diary in the CRF as items of the health observation diary as is in order to avoid overlap with adverse events evaluated by physicians.

All assessments described in this full protocol are performed as part of normal clinical practice or standard practice guidelines for the participant population and healthcare provider specialty in the countries where this non-interventional study is being conducted.

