8.3.8. Adverse events

Occurrence of adverse events from the date of the fourth vaccination with this product to the end date of the observation period should be confirmed, and the following information should be entered. Participant condition must be observed after vaccination with this product for a certain period of time, and if acute reactions such as shock and anaphylaxis are observed, appropriate measures should be taken and the details should be recorded as adverse events.

PFIZER CONFIDENTIAL

CT24-WI-JPN-GPSP01-RF08 7.0 Non-Interventional Study Protocol Template for Primary Data Collection Study

15-Sep-2022

Page 16 of 35

The information in the health observation diary (see Section 8.3.9) collected from the parents (or legal guardians) of participants should be reviewed. If there are any records other than the symptoms at the vaccination site and general symptoms specified in the diary (including COVID-19 information), the details should be verified as needed, and should be recorded as adverse events. The investigator should record the symptoms at the vaccination site (local reactions) and general symptoms including pyrexia (systemic reactions) specified in the health observation diary in the CRF as is, while avoiding overlap with adverse events evaluated by physicians.

Also, further investigation should be separately conducted, if deemed necessary by Pfizer, for participants who experienced serious adverse reaction, or adverse reactions not listed in the package insert.

- Presence or absence of adverse event
- Name of adverse event
- Severity
- Date of occurrence
- Presence or absence of treatment
- Seriousness
- Outcome (including the date of outcome)
- Causal relationship to this product

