8.3.9. Reactogenicity events (local reactions and systemic reactions) (health observation diary)

A health observation diary will be distributed to the parents (or legal guardians) of participants participating in this study, and they will be requested to record information on reactogenicity events after vaccination with this product. Reactogenicity events are defined as local reactions (symptoms at the vaccination site) and systemic reactions (general symptoms including pyrexia).

If participants are younger than 2 years of age at the time of the fourth vaccination with this product, the parents (or legal guardians) of participants will observe the participant for local reactions (injection site tenderness, redness, and injection site swelling) and systemic reactions (pyrexia, decreased appetite, somnolence, and irritability) in participants for 7 days after vaccination with this product and record them in the diary (if symptoms persist for 8 days and more, the date of symptom resolution should be recorded).

If participants are 2 years or older at the time of the fourth vaccination with this product, the parents (or legal guardians) of participant will observe participants for local reactions (injection site pain, redness, and injection site swelling) and systemic reactions (pyrexia, vomiting, diarrhoea, headache, malaise, chills, myalgia and arthralgia) for 7 days after vaccination with this product and record them in the diary (if symptoms persist for 8 days and more, the date of symptom resolution should be recorded).

The investigator will collect the health observation diary after the end of the observation period (collection by mail is also acceptable). If there are records other than symptoms at the vaccination site and general symptoms specified in the diary (including the COVID-19 information), check the details of the information (or confirm by telephone, etc.) as needed and record them as adverse events. The investigator should record the symptoms at the vaccination site (local reactions) and general symptoms including pyrexia (systemic reactions) specified in the health observation diary in the CRF as items of the health observation diary as is, while avoiding overlap with adverse events evaluated by physicians.

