8.7.2. Safety analysis

The events entered in the CRF submitted by the investigator for which the causal relationship with this product cannot be ruled out will be handled as adverse reactions, and the number and proportion of participants with adverse reactions ([%]: number of participants with adverse reactions/number of participants included in safety analysis) will be tabulated. Exploratory analyses will be performed as needed.

8.7.3. Analysis of reactogenicity events (local reactions and systemic reactions [health observation diary])

Local reactions and systemic reactions recorded in the health observation diary collected by the investigator from study participants will be handled as reactogenicity events, and the number and proportion of participants with each event will be tabulated. Exploratory analyses will be performed as needed.

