10. MANAGEMENT AND REPORTING OF ADVERSE EVENTS/ADVERSE REACTIONS

10.1. Records and report requirements

The table below summarizes the requirements for recording safety events on the CRF and for reporting safety events on the non-interventional study (NIS) adverse event monitoring (AEM) Report Form to Pfizer Safety. These requirements are delineated for three types of events: (1) serious adverse events (SAEs); (2) non-serious AEs (as applicable); and (3) scenarios involving drug exposure, including exposure during pregnancy, exposure during breastfeeding, medication error, overdose, misuse, extravasation, lack of efficacy, and occupational exposure. These events are defined in the section “Definitions of safety events.”

Safety event	Recorded on the CRF	Reported on the NIS AEM Report Form to Pfizer Safety within 24 hours of awareness
SAE	All	All
Non-serious AE	All	None
Scenarios involving exposure to a drug under study, including exposure during pregnancy, exposure during breastfeeding, medication error, overdose, misuse, extravasation, lack of efficacy, and occupational exposure	All (regardless of whether associated with an AE), except occupational exposure	All (regardless of whether associated with an AE) Note: Any associated AE is reported together with the exposure scenario.

For each AE, the investigator must pursue and obtain information adequate both to determine the outcome of the AE and to assess whether it meets the criteria for classification as a SAE (refer to section “Serious Adverse Events” below).

Safety events listed in the table above must be reported to Pfizer within 24 hours of awareness of the event by the investigator **regardless of whether the event is determined by the investigator to be related to this product**. In particular, if the SAE is fatal or life-threatening, notification to Pfizer must be made immediately, irrespective of the extent of available event information. This timeframe also applies to additional new (follow-up) information on previously forwarded safety event reports. In the rare situation that the investigator does not become immediately aware of the occurrence of a safety event, the investigator must report the event within 24 hours after learning of it and document the time of his/her first awareness of the events.

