10.4. Definitions of safety events

10.4.1. Adverse events

An AE is any untoward medical occurrence in a participant administered a medicinal product. The event need not necessarily have a causal relationship with the product treatment or usage. Examples of AEs include but are not limited to:

- Abnormal test findings (see below for circumstances in which an abnormal test finding constitutes an AE);
- Clinically significant signs and symptoms;
- Changes in physical examination findings;
- Hypersensitivity;
- Progression/worsening of underlying disease;
- Lack of efficacy;
- Drug abuse;
- Drug dependency.

Additionally, for medicinal products, they may include the signs or symptoms resulting from:

- Drug overdose;
- Drug withdrawal;
- Drug misuse;
- Off-label use;
- Drug interactions;
- Extravasation;
- Exposure during pregnancy;
- Exposure during breastfeeding;
- Medication error;
- Occupational exposure.

PFIZER CONFIDENTIAL

CT24-WI-JPN-GPSP01-RF08 7.0 Non-Interventional Study Protocol Template for Primary Data Collection Study

15-Sep-2022

Page 28 of 35

Abnormal test findings

The criteria for determining whether an abnormal objective test finding should be reported as an AE are as follows:

- Test result is associated with accompanying symptoms, and/or
- Test result requires additional diagnostic testing or medical/surgical intervention, and/or
- Test result leads to a change in study dosing or discontinuation from the study, significant additional concomitant drug treatment, or other therapy, and/or
- Test result is considered to be an AE by the investigator or Pfizer.

Merely repeating an abnormal test, in the absence of any of the above conditions, does not constitute an AE. Any abnormal test result that is determined to be an error does not require reporting as an AE.

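### The diary symptom lists change at age 2, the same cut as the any-adverse-reaction row by age, so the two age lines count different early non-serious symptoms

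*SAP*

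**What the plan says.** **Diary lists.** Protocol 8.3.9 gives children of 2 years and over "systemic reactions (pyrexia, vomiting, diarrhoea, headache, malaise, chills, myalgia and arthralgia) for 7 days after vaccination with this product". For children under 2, the systemic list over the same 7 days is pyrexia, decreased appetite, somnolence and irritability. SAP 8.2.3.3 repeats both lists.

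**Routing.** Under Protocol 8.1, the investigator enters listed symptoms "specified in the health observation diary in the CRF as items of the health observation diary as is in order to avoid overlap"; the overlap meant is with events that a physician has assessed. Protocol 8.3.8 covers the rest: "If there are any records other than the symptoms at the vaccination site and general symptoms specified in the diary", the details are checked as needed and recorded as adverse events.

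**Endpoints.** Protocol 8.7.3 says that diary reactions "collected by the investigator from study participants will be handled as reactogenicity events". SAP 6.1 keeps reactogenicity events as a separate endpoint and defines adverse reactions as those adverse events that the physician considers causally related.

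**Tables.** Protocol 8.7.2 defines the adverse reaction proportion as "number of participants with adverse reactions/number of participants included in safety analysis". SAP 8.2.3.1.1 tabulates adverse reactions by SOC and PT without an age split. SAP 5.4 cuts age at 2 years, and SAP 8.2.3.5 states that "Participants with at least one adverse reaction will be summarized in terms of n and proportion by each factor defined in Section 5.4".

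**The concern.** Keeping diary reactions apart from adverse events is ordinary practice, and it does no harm when the groups being compared share one list. Here the list changes exactly at the subgroup boundary. Early non-serious vomiting would normally be able to count as an adverse reaction at 23 months but not at 25 months; for irritability it is the reverse.

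Two outputs are affected. In the any-adverse-reaction row by age, each line admits a different set of early non-serious symptoms, so a reader may take a recording difference for an age effect. In the pooled SOC/PT table, a term listed for one age group gets its early non-serious cases mainly from the other group but is divided by everyone. Neither document flags this, and the limitations in Protocol 8.9 do not mention it. The tables feed the J-PSUR and the re-examination application (SAP 3).

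**Working it through.** **Step 1: which terms differ.** The under-2 list has 4 systemic items and the list for 2 years and over has 8. Only pyrexia is on both.

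- Listed only at 2 and over (7): vomiting, diarrhoea, headache, malaise, chills, myalgia, arthralgia.
- Listed only under 2 (3): decreased appetite, somnolence, irritability.
- Listed at both ages: pyrexia, redness, swelling. Injection site pain (2 and over) and tenderness (under 2) are local counterparts, so that complaint also goes to the diary at both ages.

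**Step 2: how an early non-serious event is normally routed.**

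| Term | Under 2 | 2 and over |
|---|---|---|
| The seven | adverse event, possible adverse reaction | diary item |
| The three | diary item | adverse event, possible adverse reaction |
| Pyrexia, redness, swelling | diary item | diary item |

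Serious events are recorded as such at either age (Protocol 10.1), and events starting after the diary window can be adverse events at either age.

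**Step 3: the plan's own figure.** SAP 2.2.7 gives 83% for seeing at least one case at 3% incidence in 60 children. 1 − 0.97^60 = 83.9%, so it reproduces. It supposes that all 60 can contribute. If only one age group could contribute, and every event in that group were captured, the probability would be 1 − 0.97^30 = 59.9% with 30 children. With 12 or 48 children it would be 30.6% or 76.8%.

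**Step 4: illustration for the age row.** The documents give no symptom rates, age split or capture rates, so every input here is assumed. All refer to early non-serious events and are the same at both ages.

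- a, b = risk of any of the seven terms and of any of the three.
- k = probability that an unlisted event is recorded as an adverse event and judged related.
- s = the same probability for a listed event.
- c = risk of any other adverse reaction, 5%.

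With independence:

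- Under 2: 1 − (1 − ka)(1 − sb)(1 − c)
- 2 and over: 1 − (1 − kb)(1 − sa)(1 − c)
- Difference: (1 − c)(k − s)(a − b)

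For a = 20% and b = 5%:

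| k | s | Under 2 | 2 and over | Difference (points) |
|---|---|---|---|---|
| 1 | 0 | 24.0% | 9.75% | 14.25 |
| 0.5 | 0 | 14.5% | 7.4% | 7.1 |
| 0.5 | 0.25 | 15.57% | 12.01% | 3.56 |
| 0.1 | 0 | 6.9% | 5.5% | 1.4 |
| k = s | | | | 0 |

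Swapping a and b reverses the sign; a = b also gives zero.

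**Step 5: illustration for the pooled table.** Let f be the share of children under 2 (20% to 50%) and p = 10% the early non-serious risk at every age. Vomiting as an adverse reaction is p[fk + (1 − f)s]. At k = 1, s = 0 this is 0.10 × 0.2 = 2.0% to 0.10 × 0.5 = 5.0%. At k = 0.5, s = 0 it is 1.0% to 2.5%. Decreased appetite is p[(1 − f)k + fs]; at k = 1, s = 0 it is 8.0% (f = 0.2) to 5.0% (f = 0.5). When k = s, both reduce to pk and the age mix no longer matters.

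**The case against.** *The routing is not absolute.* This stands. Protocol 10.1 introduces its table with "The table below summarizes the requirements for recording safety events on the CRF", and that table puts all non-serious adverse events on the CRF. Protocol 10.4.1 says "An AE is any untoward medical occurrence in a participant administered a medicinal product". The instruction to avoid overlap could mean only that one event is not entered twice. Unlisted entries are checked only as needed, and the diary form itself is not in the documents. So k may be well below 1 and s above 0. Equal capture would remove the effect, but nothing in the plan secures it.

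*Incompleteness comes from the deliberate separation of diary and adverse events, not from the age lists.* This stands in part. Pyrexia, redness and swelling go to the diary at both ages, so their adverse reaction proportions leave out diary events too. They do not distort the age comparison. What is particular to the ten terms is a numerator drawn mainly from one age group over an all-age denominator.

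*The events are shown elsewhere and the study is descriptive.* Both are true: SAP 8.2.3.3 reports them by age-specific list, and SAP 4 rules out tests. But those tables do not make the adverse reaction row comparable.

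*Chance would swamp it.* At 15% incidence the standard error of an age difference is √(0.15 × 0.85 × (1/30 + 1/30)) = 9.2 points with 30 and 30 children, and 11.5 points with 12 and 48. Most of the illustrated differences are smaller. This limits the practical harm, but a recording artefact does not shrink with more children, and a descriptive table gives no warning of it.

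**Conclusion.** The concern holds in a limited form. For early non-serious events of ten systemic terms, following the plan normally gives an any-adverse-reaction row whose two age lines count different symptoms, and pooled proportions whose numerator comes mainly from one age group. This rests on reading the symptoms specified in the diary as the age-specific lists, which Protocol 8.3.9 and SAP 8.2.3.3 support.

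Size and direction are unknown. They depend on symptom rates, on how many unlisted events are recorded and judged related, and on how often physicians also enter listed symptoms as adverse events. The figures above only show how the result moves with those assumptions.

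Three stronger readings are not supported:

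- *That seven terms against three must inflate the under-2 line.* The documents give no rates, and the sign depends on a − b and k − s.
- *That listed symptoms can never be adverse reactions, or that data are lost.* Serious, late and possibly physician-evaluated events can still count, and the diary events are tabulated separately.
- *That an inference is invalid.* No test is planned.

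The harm is a misleading subgroup line and pooled proportions that are easily misread. It is worth correcting because the correction is cheap.

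**What to change.** 1. **SAP 8.2.3.5.** Keep the any-adverse-reaction row. Footnote the age factor as not directly comparable because the diary lists differ by age. Add one any-adverse-reaction row by age that leaves out, in both age groups, non-serious events of the ten terms with onset from the day of vaccination to Day 7. Serious events, later onsets and all other terms stay in. Take the window from the onset rows in SAP 8.2.3.3.1, because the matching sentence in 8.2.3.3.2 names local reactions. Name the PTs used for each term, since Protocol Table 4 notes that fatigue appears as malaise in the diary.
2. **SAP 8.2.3.1.1.** Keep the overall proportion and its denominator. Also show the ten PTs by age group over the age-group denominators. Footnote that diary-listed reactions, including those listed at both ages, are reported in the reactogenicity tables.

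The added row is comparable with respect to the ten terms by construction: it removes the terms that are routed differently. That does not show how large the distortion was.

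Cost: SAP wording and a few table rows. Date of occurrence, seriousness and causal relationship are already collected (Protocol 8.3.8), so no new data are needed even though SAP version 2.0 records enrollment as complete. The downside is extra rows with small counts.
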